8.3 Multiple DEB-TACE Procedures Targeting Different Vascular Territories

Sequential DEB-TACE procedures may be offered in the following settings:

- A. Multifocal HCC (UNOS T2 or T3 disease; no radiographic evidence of macrovascular invasion or extracapsular extension).
- B. Single HCC greater than 3 cm (UNOS T2 or T3 disease without radiographic evidence of macrovascular invasion or extracapsular extension).
- C. More than 1 segmental feeding hepatic artery branch to a lesion of any size.

Patients with lesions that meet at least one of these criteria will be considered for up to four DEB-TACE procedures that will be performed approximately 1 month apart. Longer intervals between the procedures may be necessary in order to allow patients to regain pre-TACE liver function and performance status. Intervals between DEB-TACE procedures up to 90 days will be allowed. The timing of DEB-TACE will be determined by the treating interventional radiologist and hepatologist or medical oncologist. The number of procedures (up to 4 total) will be based on the number, location, and size of the lesions as well as on the hepatic arterial supply to the lesions. This information will be obtained from the pre-procedure cross-sectional imaging (CT or MRI) and hepatic artery angiography. This step-wise approach is intended to target the entire tumor vascular supply in a step-wise fashion prior to assessing response to therapy (Table 2).

The maximum administered doxorubicin dose per DEB-TACE procedure will be 100mg (50 mg per each 2 ml vial). The maximum administered dose as a result of four DEB-TACE procedures will be 400 mg.

8.4 Follow-Up Assessments

Vast majority of the adverse effects of DEB-TACE are expected to occur within 30 days of treatment. For the first month following each DEB-TACE, the patient's progress will be monitored at bi-weekly intervals at the gastrointestinal oncology site committee by a team consisting of medical oncologists and interventional radiologists.

8.4.1 Patients with Single DEB-TACE Procedure

The following laboratory testing will be performed 1, 7±4, 30±7, 90±14, 180±14, 270±14, and 360±14 days following DEB-TACE: CBC, coagulation panel, BUN, creatinine, and liver function tests. Serum alpha-fetoprotein testing will start approximately 30 days following last planned DEB-TACE procedure. Any abnormal lab values will be followed up as clinically indicated. Laboratory tests may be performed at UCSF or at a local lab.

Seven ±4 days following DEB-TACE patients will have clinic follow up in Interventional Radiology for toxicity monitoring including reviewing the laboratory results above. Any expected or unexpected AEs will be discussed with the study PI or a designated co-investigator. Further testing and/or treatment will be coordinated by the study PI or a designated co-investigator if clinically appropriate (see section 7).

Cardiac function assessment monitoring using echocardiogram will be obtained approximately 30 days following the DEB-TACE procedure.

Patients will be seen in clinic approximately one month after the DEB-TACE procedure. During this visit, interim medical history will be obtained, and a physical examination will be performed. This will include (but will not be limited to) cardiopulmonary evaluation and an abdominal exam. Subsequently, patients will be followed in clinic at approximately 3 month intervals until 360 days following DEB-TACE.

Approximately one month after DEB-TACE procedure, patients will undergo repeat cross-sectional imaging with multi-phase contrast-enhanced CT or MRI of the abdomen. Subsequent imaging will be performed at approximately 3 month-intervals until 360 days following DEB-TACE. Standard clinical practices will be adhered to during the follow-up period.

Response to treatment will be assessed according to the RECIST version 1.1 and mRECIST criteria (see section 9.2).

Patients will be removed from study and follow-up assessments will stop prior to 360 days following DEB-TACE if a patient:

- a) requires > 4 DEB-TACE procedures
- b) requires another anti-cancer treatment modality such as ablation, surgery, or conventional TACE
- c) receives a liver transplant
- d) develops untreatable intrahepatic or extrahepatic disease progression
- e) experiences unacceptable toxicity (see section 10.0). All serious adverse events will be followed until the SAE has been resolved.

Pathology report describing the extent of HCC in the liver explant will be reviewed for the subset of patients who undergo LT.

8.4.2 Patients with Multiple DEB-TACE Procedures

The following laboratory testing will be performed 1 and 7±4 days following each DEB-TACE: CBC, coagulation panel, BUN, creatinine, and liver function tests. Any abnormal lab values will

be followed up as clinically indicated. Laboratory tests may be performed at UCSF or at a local lab.

Seven ± 4 days following DEB-TACE patients will have clinic follow up in Interventional Radiology for toxicity monitoring including reviewing the laboratory results above. Any expected or unexpected AEs will be discussed with the study PI or a designated co-investigator. Further testing and/or treatment will be coordinated by the study PI or a designated co-investigator if clinically appropriate (see section 7).

Cardiac function assessment monitoring using echocardiogram will be obtained approximately 30 days following last planned DEB-TACE procedure.

Candidacy for repeat DEB-TACE (sessions 2-4) will be based on laboratory and clinical follow-up on day 7 ± 4 and on the day of scheduled repeat DEB-TACE (sessions 2-4). The decision to delay or cancel subsequent planned DEB-TACE procedures would be at the discretion of the treating interventional radiologist, hepatologist, or medical oncologist. This decision will be based on currently used clinical practice standards at UCSF.

Upon completion of 2-4 planned DEB-TACE treatment sessions, the following laboratory testing will be performed 1, 7 ± 4 , 30 ± 7 , 90 ± 14 , 180 ± 14 , 270 ± 14 , and 360 ± 14 days following DEB-TACE: CBC, coagulation panel, BUN, creatinine, and liver function tests. Serum Alpha-fetoprotein testing will start 30 days following last planned DEB-TACE procedure. Any abnormal lab values will be followed up as clinically indicated.

Patients will be seen in clinic approximately one month after the last planned DEB-TACE procedure. During this visit, interim medical history will be obtained, and a physical examination will be performed. This will include (but will not be limited to) cardiopulmonary evaluation and an abdominal exam. Subsequently, patients will be followed in clinic at approximately 3 month intervals until 360 days following DEB-TACE.

Approximately one month after last planned DEB-TACE procedure, patients will undergo repeat cross-sectional imaging with multi-phase contrast-enhanced CT or MRI of the abdomen. First follow-up imaging study will be obtained no more than 6 months following the first DEB-TACE procedure. Subsequent imaging will be performed at approximately 3 month-intervals until 360 days following DEB-TACE. Standard clinical practices will be adhered to during the follow-up period.

Response to treatment will be assessed according to RECIST version 1.1 and mRECIST criteria (see section 9.2).

Patients will be removed from study and follow-up assessments will stop prior to 360 days following DEB-TACE if a patient:

- a) requires > 4 DEB-TACE procedures
- b) requires another anti-cancer treatment modality such as ablation, surgery, or conventional TACE

- c) receives a liver transplant
- d) develops untreatable intrahepatic or extrahepatic disease progression
- e) experiences unacceptable toxicity (see section 10.1). All serious adverse events will be followed until the SAE has been resolved.

Pathology report describing the extent of HCC in the liver explant will be reviewed for the subset of patients who undergo LT.

8.5 Ancillary Therapy

Patients should receive full supportive care, including transfusions of blood and blood products, antibiotics, analgesics, antiemetics, etc., when appropriate.

Patients taking concomitant medications known to be metabolized by the liver should be closely observed for side effects. Patients taking narrow therapeutic index medications that are hepatically metabolized should be monitored proactively. These medications include warfarin, phenytoin, quinidine, carbamazepine, phenobarbital, cyclosporin and digoxin. No medication is specifically prohibited, and there are no specific dietary restrictions.

9.0 CRITERIA FOR EVALUATION

The primary endpoints of this study are to evaluate the safety and efficacy of DEB-TACE in patients with marginal hepatic function.

9.1 Safety

Safety data will be collected as a part of this clinical protocol. The assessments will be based on post-procedure clinical evaluations, laboratory tests, and imaging studies (see section 8 for more details). Six weeks after all 17 patients have been treated with at least one DEB-TACE, data on DEB-TACE safety profile will be analyzed. Final safety analysis will be performed 6 weeks after all 51 patients have been treated with at least one DEB-TACE.

9.2 Efficacy

Evaluation of the treatment response will be based on contrast-enhanced cross-sectional imaging of the abdomen (CT or MRI) performed one month following last planned DEB-TACE procedure within six months of the first DEB-TACE procedure. Treatment response will be evaluated according to both the RECIST version 1.1 and mRECIST criteria. Whenever possible, the same imaging modality (CT or MRI) will be used for pre- and post-treatment assessments.

9.2.1 RECIST Definitions

Measurable Disease: The presence of at least one measurable lesion. If the measurable disease is restricted to a solitary lesion, its neoplastic nature should be confirmed by cytology/histology.

Measurable Lesion: The lesion can be accurately measured in at least one dimension [longest diameter to be recorded] as ≥ 10 mm with spiral CT scan.

Nonmeasurable Lesion: All other lesions, including small lesions [< 10 mm with spiral CT scan] and truly nonmeasurable lesions.

Complete Response (CR): Disappearance of all target lesions

Partial Response (PR): 30% decrease in the sum of the longest diameter of target lesions

Stable Disease (SD): Small changes that do not meet the criteria for CR, PR, or PD

Progressive Disease (PD): 20% increase in the sum of the longest diameter of target lesions

9.2.2 RECIST Guidelines

- All measurements should be taken and recorded in metric notation, using a ruler or calipers.
- All baseline evaluations should be performed as closely as possible to the beginning of treatment and never more than 4 weeks before the beginning of the treatment.
- Assessment will be performed using conventional imaging methods (CT, MRI).
- The same method of assessment and the same technique should be used to characterize each identified and reported lesion at baseline and during follow-up.
- Up to three measurable lesions will be identified as target lesions. Target lesions will be selected on basis of size (lesions with the longest diameter) and their suitability for accurate repeated measurements (lesions can be located/identified during follow-up as well as baseline).
- Target lesions will be measured in one dimension. A sum of the longest diameter (LD) for all target lesions will be calculated and reported as the baseline sum LD. The baseline sum LD will be used as reference by which to characterize the objective tumor.

All other lesions (or sites of disease) should be identified as non-target lesions and should also be recorded at baseline. Measurements of these lesions are not required, but the presence or absence of each should be noted throughout follow-up.

9.2.3 mRECIST Definitions (See Appendix 4)

Measurable Disease: The presence of at least one measurable lesion.

Measurable Lesion: The lesion can be accurately measured in at least one dimension [longest diameter to be recorded] as ≥ 10 mm with spiral CT or MRI scan.

Nonmeasurable Lesion: All other lesions, including small lesions [<10 mm with spiral CT scan or MRI] and truly nonmeasurable lesions (infiltrative lesions).

Complete Response (CR): Disappearance of any intratumoral arterial enhancement in all target lesions

Partial Response (PR): 30% decrease in the sum of diameters of viable (enhancement in the arterial phase) target lesions, taking as reference the baseline sum of the diameters of target lesions

Stable Disease (SD): Any cases that do not qualify for either partial response or progressive disease

Progressive Disease (PD): An increase of at least 20% in the sum of the diameters of viable (enhancing) target lesions, taking as reference the smallest sum of the diameters of viable (enhancing) target lesions recorded since treatment started

9.2.4 mRECIST Guidelines (See Appendix 4)

- All eligible patients with measurable disease *at baseline* will be included in the analysis for efficacy.
- All measurements should be taken and recorded in metric notation, using a ruler or calipers.
- All baseline evaluations should be performed as closely as possible to the beginning of treatment and never more than 4 weeks before the beginning of the treatment.
- Assessment will be performed using conventional imaging methods (CT, MRI).
- The same method of assessment and the same technique should be used to characterize each identified and reported lesion at baseline and during follow-up.
- Up to three measurable lesions will be identified as target lesions. Target lesions will be selected on basis of size (lesions with the longest diameter) and their suitability for accurate repeated measurements (lesions can be located/identified during follow-up as well as baseline).
- Target lesions will be measured in one dimension. A sum of the longest diameter (LD) for all target lesions will be calculated and reported as the baseline sum LD. The baseline sum LD will be used as reference by which to characterize the objective tumor.
- All other lesions (or sites of disease) should be identified as non-target lesions and should also be recorded at baseline. Measurements of these lesions are not required, but the presence or absence of each should be noted throughout follow-up.

The measurement of the longest diameter of the viable tumor may be challenging in lesions showing partial internal necrosis. The following points should be taken into account in such cases:

- The measurement of the viable tumor should be performed on CT or MRI obtained in the arterial phase, when the contrast between viable vascularized tumor tissue and nonenhancing necrotic tissue is the highest.
- The longest diameter of the viable tumor is not necessarily located in the same scan plane in which the baseline diameter was measured: a thorough careful evaluation of the CT or MRI scans is required.
- The measurement of the viable tumor diameter should not include any major intervening areas of necrosis.

10.0 CRITERIA FOR STUDY TERMINATION

10.1 STOPPING RULES FOR SAFETY.

10.1.1 Rationale

A retrospective analysis of toxicity of conventional TACE method for UCSF patients with HCC and hepatic dysfunction, which included 252 patients and 446 TACE procedures was recently completed (24). This cohort included 166 patients who met the more stringent inclusion criteria for the current study. These patients underwent a total of 260 TACE procedures. In this patient cohort, 20 patients (12%) developed NCI CTCAE grade 4 hepatotoxicity that persisted 1 month following TACE. Of note, patients who had irreversible grade 4 hyperbilirubinemia with or without grade 4 transaminitis had a 27.7% rate of mortality or required an urgent liver transplant within 6 weeks of TACE. This rate was higher than that for patients who had grade 4 transaminitis without grade 4 hyperbilirubinemia, 11.1% of whom died or required an urgent liver transplant within 6 weeks of TACE. These findings suggested that irreversible hyperbilirubinemia was a more robust predictor of mortality or TACE-induced liver failure requiring salvage transplantation than transaminitis.

Based on the same retrospective study (24), a total of 2 patients (1.2%) had grade 4 renal toxicity that persisted 1 month following TACE.

Based on the same retrospective study (24), mortality rate 6 weeks following TACE was 4.8% (8 patients).

No published comparable safety data is available for DEB-TACE with regards to the patient population to be studied. However, a total of 37 patients with marginal liver function (within proposed inclusion criteria for this study) have been treated between 2011 and 2013. Their records were retrospectively reviewed. Preliminary results on adverse events following DEB-TACE are summarized in Table 1. No treatment-related deaths and no events hepatic decompensation requiring an urgent liver transplant were encountered in this patient cohort.

Stopping rules for safety were determined based on the assumption that DEB-TACE may be associated with similar rates of morbidity as conventional TACE.

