1.2 TACE Toxicity

Complication rates following TACE are high (25-45%) with the majority being reversible elevations of hepatic transaminases and serum bilirubin without an impact on long-term prognosis, however, for a small proportion of patients, irreversible hepatic decompensation occurs (15). TACE-related irreversible hepatic decompensation is described as significant and acute elevation of liver function tests, evidence of new ascites, new encephalopathy, or worsening of either. These serious complications, frequently accompanied by deterioration in clinical status, may lead to the requirement of urgent liver transplantation in eligible patients, ineligibility for and/or risk of increased toxicity from systemic therapy with sorafenib or investigational systemic therapies for HCC, or death (16). Rates of complications following conventional TACE performed for patients with marginal hepatic reserve or portal vein thrombosis have been described (16-23).

We have recently completed a retrospective record review of 252 patients with HCC and hepatic dysfunction who underwent 446 cTACE procedures at our institution between 2005 and 2009 (24). Patients were eligible for inclusion if they had one of the following criteria: pre-TACE

bilirubin ≥ 2 mg/dL, aspartate aminotransferase (AST) or alanine aminotransferase (ALT) > 5 times upper normal limit, international normalized ratio (INR) > 1.5 , creatinine > 1.2 mg/dL, platelet count $\leq 60,000/\mu\text{L}$, Model for End-Stage Liver Disease (MELD) score > 15 , Childs-Pugh class B or C, ascites, or portal venous thrombus. Hepatotoxicity was defined as one of the following: new or worsening ascites, encephalopathy, or NCI Common Terminology Criteria for Adverse Events grade 3 or 4 toxicity of bilirubin, AST, ALT, creatinine or INR. Rate and risk factors for persistent hepatotoxicity were determined using generalized estimating equation analysis.

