10.1.2 Specific Stopping Rules for Safety

Safety data will be routinely monitored and sequential safety assessments will be conducted as subjects are enrolling to the study. The study will be stopped due to safety/toxicity concern prior to interim efficacy analysis if *any* of the following 3 stopping rules are met:

1. Liver dysfunction (clinical or laboratory [total serum bilirubin], grade 4) that does not improve to baseline or \leq grade 3 within 1 month following DEB-TACE in ≥ 7 patients (12% of 51 patients).

OR

2. Renal dysfunction (clinical or laboratory [serum creatinine], grade 3 or 4) that does not improve to baseline or \leq grade 2 within 1 month following DEB-TACE in ≥ 2 patients (1.2% of 51 patients).

OR

3. Any grade 5 AE (death) attributed as at least possibly-related to study intervention in ≥ 3 patients (4.8% of 51 patients).

The stopping rules above were used to generate the following chart, which will be adhered to with regards to stopping enrollment for the reasons of severe toxicity.

Table 4. Number of patients with defined safety/toxicity for the study to be stopped during sequential and continuous safety assessments (based on binomial distribution)

Number patients enrolled in study	3	7	11	13	17	23
Number of patients with grade 4 liver dysfunction, grade 4 renal dysfunction, or study-related death	2	4	6	7	8	9
% chance of stopping enrollment if true SAE rate is $<15\%$	94%	99%	99%	99%	99%	99%
% chance of stopping enrollment if true SAE rate is $<20\%$	90%	97%	99%	99%	99%	97%
% chance of stopping enrollment if true SAE rate is $<30\%$	78%	87%	92%	94%	90%	77%

Note: the study will also be terminated early if any of the 3 stopping rules is observed.

Adverse events grade ≥ 4 will be discussed by the interventional radiologist and medical oncologist and/or hepatologist within 1 business day of being informed of the event. If at any time a patient has a fatal complication at least possibly related to treatment, the study will immediately be put on hold. At that time, the data will be reviewed by a multidisciplinary team as to the etiology. If it is determined that the death was attributed as at least possibly-related to treatment, the study investigators will meet to discuss if the study should continue.

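### Stopping rule 1 takes its limit of 7 from the rate of all persistent grade 4 hepatotoxicity, but its laboratory arm counts only bilirubin; rules 2 and 3 also differ from their benchmark events

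*Combined protocol and SAP*

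**What the plan says.** Section 10.1.1 takes its benchmarks from the institution's retrospective review of conventional TACE: "This cohort included 166 patients who met the more stringent inclusion criteria for the current study". It gives three rates in those patients:

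- Liver: "20 patients (12%) developed NCI CTCAE grade 4 hepatotoxicity that persisted 1 month following TACE".
- Kidney: 2 patients (1.2%) with grade 4 renal toxicity still present at 1 month.
- Death: "mortality rate 6 weeks following TACE was 4.8% (8 patients", with no restriction by cause or attribution.

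Section 1.2 describes the same review and defines its hepatotoxicity as new or worse ascites, encephalopathy, or "grade 3 or 4 toxicity of bilirubin, AST, ALT, creatinine or INR". Section 10.1.1 says the safety limits assume that DEB-TACE morbidity resembles that of conventional TACE.

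Section 10.1.2, repeated in the Abstract, sets the rules:

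- Rule 1 stops the study at 7 or more patients, annotated as 12% of 51. It counts "Liver dysfunction (clinical or laboratory [total serum bilirubin], grade 4", unresolved at 1 month.
- Rule 2 stops at 2 or more patients, annotated as 1.2% of 51. It counts grade 3 or 4 renal dysfunction unresolved at 1 month.
- Rule 3 stops at 3 or more patients, annotated as 4.8% of 51. It counts "Any grade 5 AE (death) attributed as at least possibly-related to study intervention", with no time window.

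**The concern.** A limit that is meant to express similarity to conventional TACE needs the same event on both sides. In rule 1 the percentage belongs to a wider laboratory definition than the rule counts. The review did contain patients who fall between the two definitions, since section 10.1.1 reports a separate outcome for those with "grade 4 transaminitis without grade 4 hyperbilirubinemia, 11.1% of whom died or required an urgent liver transplant within 6 weeks of TACE". An isolated grade 4 AST or ALT elevation can therefore add to the 12% without adding to the count of 7.

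Section 10.1.1 explains why bilirubin was chosen: it predicted death or salvage transplant better than transaminases did. That supports the choice of event. It does not support attaching the rate of a wider event to it, and no bilirubin-specific rate is given. At stake is whether 7 patients marks the conventional-TACE rate, as the text says, or some higher rate of the event being counted.

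**Working it through.** **Inputs.** From section 10.1.1: 166 patients, 20 with persistent grade 4 hepatotoxicity, 2 with persistent grade 4 renal toxicity, 8 deaths by 6 weeks. From section 10.1.2: limits 7, 2 and 3, each tied to 51 patients.

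**Reproducing the limits.** Take the smallest whole number above rate × 51.

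- Rule 1: 20/166 = 12.05%; 0.12 × 51 = 6.12; limit 7, as stated.
- Rule 3: 8/166 = 4.82%; 0.048 × 51 = 2.45; limit 3, as stated.
- Rule 2: 2/166 = 1.20%; 0.012 × 51 = 0.61; this rounding would give 1, while the plan has 2.

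Limits 1 and 3 are thus the full benchmark rates scaled to 51, with no adjustment for the event counted.

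**What rule 1 leaves out.** Its clinical arm still counts grade 4 clinical liver dysfunction. INR is in the review's definition, but Table 1 in section 1.2 marks grade 4 INR as not applicable, and 10.1.1 treats renal toxicity separately. The grade 4 laboratory events at issue are therefore mainly AST or ALT elevations without grade 4 bilirubin and without clinical dysfunction.

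**Matched limit for rule 1.** Let x be the number of the 20 with such isolated elevations. The matched rate is (20 − x)/166. The documents do not give x; the values below are assumptions.

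| x | Rate | Expected in 51 | Limit by the same rounding |
|---|---|---|---|
| 0 | 20/166 = 12.05% | 6.14 | 7 |
| 2 | 18/166 = 10.84% | 5.53 | 6 |
| 5 | 15/166 = 9.04% | 4.61 | 5 |
| 9 | 11/166 = 6.63% | 3.38 | 4 |
| 14 | 6/166 = 3.61% | 1.84 | 2 |

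One isolated case is enough to move the limit: 19/166 × 51 = 5.84, giving 6.

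**Can x be recovered from the text?** No. The 27.7% (hyperbilirubinemia group) and 11.1% (transaminitis-only group) come without denominators. The smallest fractions that fit are 5/18 = 27.78% (truncated) and 1/9 = 11.11%. Their denominators add to 27, more than 20, so the two groups cannot both lie within the 20. Section 10.1.1 also calls only the hyperbilirubinemia group irreversible.

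**Rules 3 and 2, side by side.**

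| Rule | Benchmark | Counted | Difference |
|---|---|---|---|
| 3 | Deaths by 6 weeks, no attribution filter | Deaths at least possibly related, no time window | Narrower by attribution, wider in time |
| 2 | Grade 4 renal, persistent | Grade 3 or 4 renal, persistent | Wider by grade |

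Table 4 pools the three event types and names only grade 4 for the kidney, so it does not match rule 2 either.

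**The case against.** The strongest defence is that bilirubin was chosen deliberately and for a stated reason, and that rule 1 is not bilirubin-only. A transaminitis-only patient who goes into liver failure would plausibly be caught by the clinical arm, or by rule 3 if a possibly related death follows. The loss may then be small: with 2 of the 20 uncounted, the limit moves only from 7 to 6. All of this stands as a bound on the size. It does not explain why the 12% was kept.

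The plan also has other safeguards. Any death at least possibly related puts the study on hold for multidisciplinary review, and grade 4 or higher events are discussed within 1 business day (10.1.2). Raised grade 3 or 4 rates are reported to the monitoring committee, and all deaths to the FDA (13.5.3). These limit the consequence, especially for rule 3, but they do not supply a matched numerical limit.

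A reader might go further than the documents allow in three ways:

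- That rule 3 counts a subset of its benchmark and so must tolerate more deaths than conventional TACE produced. It has no 6-week window, and section 14.3 keeps later serious related events reportable, so this does not follow.
- That the chance of missing excess toxicity can be calculated by applying the limits to 51 patients. The rules are worded to act before the 17-patient interim efficacy analysis, alongside Table 4, so such figures would not describe how they perform.
- That results will be published against 12% or 4.8%. Section 12.3 plans only descriptive safety summaries.

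**Conclusion.** The mismatch in rule 1 is established from the text: its limit reproduces exactly from the rate of all persistent grade 4 hepatotoxicity, while its laboratory arm is restricted to total bilirubin. The limit is looser than the stated assumption implies, unless all 20 benchmark patients would also have met the rule. The size cannot be fixed. Over the assumed range of 2 to 14 isolated cases, the matched limit runs from 6 down to 2, so the effect may be slight or large. This rests on two readings: that the 20 patients were classified by the definition in section 1.2, and that isolated AST or ALT elevation does not count as clinical liver dysfunction.

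For rule 3, the benchmark and the counted event differ in both attribution and time, so the direction of any bias is unknown and the hold after a possibly related death limits what follows. Rule 2's counted event is wider than its benchmark. The point merits a correction because a decision threshold rests on a different event. It does not show that harmful toxicity would pass unnoticed.

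**What to change.** Reconcile the Abstract, 10.1.1 and 10.1.2 so that each limit comes from the rate of the event its rule counts. There are two routes, and the choice of event is the sponsor's:

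- Re-tabulate the institution's 166 patients on the counted event. For rule 1 this is persistent grade 4 bilirubin or clinical liver dysfunction; for rule 2, the renal grades it names; for rule 3, deaths by attribution and within a stated time window.
- Keep the present benchmarks and count the events behind them.

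Then restate the percentages and patient counts, state the rounding rule used, and carry any change into Table 4, including its renal grade.

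The cost is one re-tabulation of data the institution already holds and a wording amendment. The downside is that some limits may become stricter. If past deaths cannot be attributed reliably, the plan should say so and leave rule 3 without a claimed benchmark rate.

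### Renal stopping rule 2 counts persistent grade 3 or 4 events, but the 1.2% attached to it and Table 4 count grade 4 only, and no stopping probability is given for the rule

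*Combined protocol and SAP*

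**What the plan says.** Section 10.1.1 draws its conventional-TACE benchmarks from the institution's retrospective series: "This cohort included 166 patients who met the more stringent inclusion criteria for the current study". On renal events it says that "a total of 2 patients (1.2%) had grade 4 renal toxicity that persisted 1 month following TACE". It gives the basis for the limits as follows: "Stopping rules for safety were determined based on the assumption that DEB-TACE may be associated with similar rates of morbidity as conventional TACE".

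Section 10.1.2, repeated in the Abstract, defines the event for rule 2 as "Renal dysfunction (clinical or laboratory [serum creatinine], grade 3 or 4) that does not improve to baseline or" grade 2 or lower, within 1 month of DEB-TACE. The limit is printed as "≥ 2 patients (1.2% of 51 patients").

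The three rules share one lead-in: "The study will be stopped due to safety/toxicity concern prior to interim efficacy analysis if" any of them is met. Table 4 follows and is described as generated from the rules. Its count row reads "Number of patients with grade 4 liver dysfunction, grade 4 renal dysfunction, or study-related death".

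The renal event therefore appears with two definitions:

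| Place | Renal grade counted |
|---|---|
| 10.1.1, benchmark | 4 |
| 10.1.2 and Abstract, rule 2 | 3 or 4 |
| 10.1.2, Table 4 | 4 |

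**The concern.** A limit justified by assuming morbidity similar to conventional TACE needs a conventional-TACE rate for the event it counts. Rule 2 does not have one. Persistent grade 3 events count toward the limit, but none is in the 1.2%. Rule 1, by contrast, uses grade 4 in both the rule and its benchmark.

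Two things are at stake. First, a monitoring committee cannot tell from the text whether a persistent grade 3 creatinine event counts toward every renal limit, because rule 2 and Table 4 disagree within one section. Second, two patients are enough to meet the rule and end the study. Anyone judging how often that would happen to a regimen no more nephrotoxic than conventional TACE has only the 1.2% to work from, and that rate belongs to a narrower event.

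**Working it through.** **Inputs.** From 10.1.1: 2 persistent grade 4 renal events and a cohort of 166. From 10.1.2: a limit of 2 patients, a printed 1.2% of 51, and a window before the interim efficacy analysis. From 10.2 and 12.1: 17 patients in the first stage and 51 in total. From Table 1 in 1.2: no grade 3 or 4 creatinine events in 37 DEB-TACE patients. The count of persistent grade 3 renal events in the 166 is not given, so it is varied below as an assumption.

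**Step 1: reproduce the benchmark.** 2/166 = 0.01205, or 1.2%. The printed figure is right for grade 4.

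**Step 2: check the label on the limit.** 0.012 × 51 = 0.61 patients. 2/51 = 3.9%. The limit of 2 and the 1.2% beside it are not the same quantity.

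**Step 3: look for a stated stopping probability.** The only safety probabilities are in Table 4. They are for a composite of liver events, renal events and death, at rates of 15%, 20% and 30%. None is for rule 2 alone.

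**Step 4: compute one.** With event probability p per patient, the chance that rule 2 has been met by n patients is

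P(X ≥ 2) = 1 − (1 − p)^n − n·p·(1 − p)^(n−1).

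At p = 2/166 and n = 17: 1 − 0.8138 − 0.1687 = 0.0175. At n = 51: 1 − 0.5389 − 0.3352 = 0.1259. The limit is a fixed count, so these are already cumulative, and continuous monitoring does not raise them.

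**Step 5: direction.** A patient with persistent grade 4 toxicity also meets rule 2, so the rule-2 rate in the same cohort is at least 2/166. P(X ≥ 2) increases with p, so the step 4 figures are lower bounds for the rule as written.

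**Step 6: size, under an assumed grade 3 count.**

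| Extra persistent grade 3 cases in 166 (assumed) | p | Met by 17 patients | Met by 51 patients |
|---|---|---|---|
| 0 | 2/166 = 1.2% | 1.75% | 12.6% |
| 1 | 3/166 = 1.8% | 3.7% | 23.5% |
| 2 | 4/166 = 2.4% | 6.2% | 34.9% |

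**Step 7: other evidence on the rate.** For 0 of 37, the exact one-sided 95% upper limit is 1 − 0.05^(1/37) = 7.8%. The DEB-TACE series is compatible with every row of the table, including the first. It also defines persistence at 6 weeks rather than 1 month.

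**The case against.** A reader might infer that the plan understates the false-stop risk, or that rule 2 would stop an acceptable regimen much more often than intended. The documents support neither reading.

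- **No printed figure is too low.** The plan states no stopping probability for rule 2 and sets no target for one.
- **The effect may be nil.** The grade 3 count is unreported. If it is zero, nothing in the table moves, and the only grade 3 renal data in the documents are 0 of 37.
- **The large percentages depend on the window.** The rules are worded as applying before the interim efficacy analysis, which is the 17-patient stage. There, one or two extra cases give 3.7% or 6.2%. The 51-patient column needs the rule to run to the end. The text leaves this open: the percentages are written against 51, accrual continues during the interim analysis, and Table 4 runs to 23 patients.
- **The limit does not follow from 1.2% anyway.** Rules 1 and 3 look like the benchmark times 51, rounded up (12% gives 6.1, limit 7; 4.8% gives 2.4, limit 3). The same step would give rule 2 a limit of 1. Rates of 4/166 to 6/166 give 1.2 to 1.8 and so a limit of 2. The limit cannot be called too tight for the wider event.
- **Rule 2 is not unusually quick to stop.** By 51 patients and at their own benchmarks, rule 1 (20/166, limit 7) is met 41.8% of the time and rule 3 (8/166, limit 3) 44.8%. Both exceed rule 2's 34.9% at 4/166. Counting more renal events can also be defended as caution.

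All of these stand as limits on what can be claimed about size. None removes the conflict in grade, the missing rate for the event counted, or the wrong percentage beside the limit.

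**Conclusion.** The point holds as a mismatch of definitions with a known direction and an unknown size. The rate cited for rule 2 belongs to a narrower event than the rule counts, Table 4 follows the narrower definition, and the printed percentage does not correspond to the limit (0.6 patients against 2).

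A stopping probability derived from the cited rate can only be a floor at conventional-TACE toxicity. How far the true figure lies above it depends on a count that the documents omit. Within the assumed range of zero to two extra cases, the chance is unchanged at one end. At the other it is about 3.6 times as large by 17 patients (6.2/1.75) and 2.8 times by 51 (34.9/12.6).

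These figures treat patients as independent and take k/166 as the true rate, ignoring its sampling error. They do not show that the limit of 2 is wrong, and which grades should count is not a question that this check can settle.

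**What to change.** 1. Reconcile the renal grade in 10.1.1, in rule 2 (10.1.2 and the Abstract) and in Table 4. The sponsor and the monitoring committee decide which grades count.
2. Recount the 166-patient cohort under the chosen definition, including the 1-month improvement criterion, and replace the 1.2% with that rate. The recount looks feasible, because the retrospective review already classed "NCI Common Terminology Criteria for Adverse Events grade 3 or 4 toxicity of bilirubin, AST, ALT, creatinine or INR" as hepatotoxicity (1.2), so creatinine was graded at both levels.
3. Correct the label that equates two or more patients with 1.2% of 51.
4. State whether rule 2 ends at the interim efficacy analysis or runs to 51 patients, and give its exact stopping probability at the recounted rate for that window.

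The cost is a recount of existing data and edits to 10.1.1, 10.1.2 with Table 4, and the Abstract. No patients or procedures are added. The drawback is that the stated stopping probability may look less favourable than one based on 1.2%.
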